7.6.2.6 Subgroup Analyses

Subgroups analyses of key efficacy measures (primary endpoint of CSBPAR by Month 6 and key secondary endpoints of CSBPAR by 12 and 24 months) will be performed. Similar analyses will be performed for subject and graft survival by Month 24 if there are at least 5 subjects across treatment groups who died or experienced graft loss during the 24 month-treatment period (see Section 7.1).

Summary statistics for the above efficacy measures by treatment group will be presented for only those subgroup categories that consist of 10% or more of the total study population. No statistical tests will be performed for subgroups.

Table 7.6.2.6-1: Subgroup categories for Key Endpoints

Type of Characteristic	Subgroup factor	Categories
Donor Characteristics	Donor Condition	Living Donor
		Deceased Donor
Recipient Characteristics	Recipient Gender	Male
		Female
Recipient Characteristics	Recipient Race	White
		Black
		Other
Recipient Characteristics	Recipient Diabetic Status	Diabetic
		Non-Diabetic

7.7 Safety

Safety analysis will be based on all randomized, transplanted, and treated subjects (as treated population). All AEs will be summarized and listed by treatment groups. SAEs and AEs that result in discontinuation of the study drug will also be tabulated in detail. Laboratory marked abnormalities that are determined as “critically” out of range per the central laboratory manual, will be summarized descriptively. There will be no statistical testing of group differences with respect to frequencies of adverse events or laboratory marked abnormalities or changes in clinical laboratory tests from baseline (last measurement prior to first dose date/time).

All safety summaries except those for reports of death, graft loss, PTLD, malignancies, and serious infections, will be based only on data available at each of the scheduled analysis time points, applying ‘last dose date + 56’ cut counting rules. For events of death, graft loss, PTLD, malignancies, and serious infections, two different summaries will be prepared. The first summary will be based only on data available applying ‘last dose date + 56’ cut counting rules. The second summary will be based on all available data without applying ‘last dose date + 56’ cut counting rules.

The frequencies and exposure adjusted incidence rates using person-year method will be summarized by treatment regimen groups and overall.

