## **6.6 Potential Drug Induced Liver Injury (DILI)**

Wherever possible, timely confirmation of initial liver-related laboratory abnormalities should occur prior to the reporting of a potential DILI event. All occurrences of potential DILIs, meeting the defined criteria, must be reported as SAEs (see [Section 6.1.1](#) for reporting details).

Potential drug induced liver injury is defined as:

- a) A serum AT (ALT or AST) elevation  $> 3$  times ULN  
AND
- b) A serum total bilirubin  $> 2$  times ULN, without initial findings suggestive of cholestasis (e.g., an elevated serum alkaline phosphatase),  
AND
- c) No other immediately apparent possible causes of AT elevation and hyperbilirubinemia, including, but not limited to, viral hepatitis, pre-existing chronic or acute liver disease, or the administration of other drug(s) known to be hepatotoxic.

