7.7.2 Laboratory Test Analysis

Laboratory marked abnormalities as identified using pre-defined criteria (see [APPENDIX 4](#)), will be descriptively summarized with frequency and percentage. All laboratory values of a laboratory analyte will be listed for subjects with at least one marked abnormality for this parameter will be listed (independent of study period).

All available laboratory parameters included in the Hematology and Chemistry Panels in protocol Section 5.3.6.1 will also be summarized over time (with mean, SD, median, minimum, Q25, Q75, and maximum).

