APPENDIX 4 MARKED LABORATORY ABNORMALITY CRITERIA

Thresholds for defining markedly abnormal laboratory analyte values (per National Cancer Institute Common Terminology Criteria for Adverse Events (NCI CTCAE), version 4.0 (published 29-May-2009)).

Analyte	Formatted Value	Code	Lower threshold for Marked Abnormality			Upper threshold for Marked Abnormality		
			US conventional unit	Conventional units	SI Units	US conventional unit	Conventional units	SI Units
Hemoglobin	Hemoglobin	HB	< 8.0g/dL	< 8.0g/dL	< 80g/L	More than 4.0g/dL > ULN*	More than 4.0g/dL > ULN*	More than 40g/L > ULN
White blood cell (WBC) count	Leukocytes	WBC	< 2.0 x 10 [*] 9C/L (10 * 9 C/L = 10 * 3C/uL)	< 2,000/mm ³	< 2.0 x 10 [*] 9C/L			
Absolute lymphocytes	Lymphocytes (absolute)	LYMPA	< 0.5 x 10 [*] 9C/L (10 * 9C/L = 10 * 3C/uL)	< 500/mm ³	< 0.5 x 10 [*] 9C/L	> 20 x 10 [*] 9C/L	> 20,000/mm ³	> 20 x 10 [*] 9C/L
Absolute neutrophils	Neutrophils (absolute)	NEUTA	< 1.0 x 10 [*] 9C/L (10 * 9C/L = 10 * 3C/uL)	< 1,000/mm ³	< 1.0 x 10 [*] 9C/L			
Platelets	Platelet Count	PLAT	< 50 x 10 [*] 9C/L (10 * 9C/L = 10 * 3C/uL)	< 50,000/mm ³	< 50 x 10 [*] 9C/L			
Serum creatinine	Creatinine	CREAT				> 3.0mg/dL	> 3.0mg/dL	> 265umol/L
Urinary protein/creatinine ratio	Protein/Creatinine Ratio	PRCRR				≥ 3500mg/mg creatinine	≥ 3.5g/mg creatinine	> 395mg/mmol creatinine
Serum sodium [Na]	Sodium, Serum	NA	< 130mEq/L	< 130mEq/L	< 130mmol/L	> 155mEq/L	> 155mEq/L	> 155mmol/L

Analyte	Formatted Value	Code	Lower threshold for Marked Abnormality			Upper threshold for Marked Abnormality		
Serum potassium [K]	Potassium, Serum	K	< 3.0mEq/L	< 3.0mEq/L	< 3.0mmol/L	> 6.0mEq/L	> 6.0mEq/L	> 6.0mmol/L
Bicarbonate [HCO ₃]	Bicarbonate	HCO3	< 11mEq/L	< 11mmol/L	< 11mmol/L			
Serum calcium [Ca]	Calcium, Total	CA	< 7.0mg/dL	< 7.0mg/dL	< 1.75mmol/L	> 12.5mg/dL	> 12.5mg/dL	> 3.1mmol/L
Serum magnesium [Mg]	Magnesium, Serum	MG	< 0.8mEq/L	< 0.9mg/dL	< 0.4mmol/L	> 2.5mEq/L	> 3.0mg/dL	> 1.23mmol/L
Serum phosphorus [P]	Phosphorus, Inorganic	PHOS	< 2.0mg/dL	< 2.0mg/dL	< 0.6mmol/L			
Serum albumin	Albumin	ALB	< 2.0g/dL	< 2.0g/dL	< 20g/L			
Serum uric acid	Uric Acid	URIC				> 10.0mg/dL	> 10.0mg/dL	> 0.59mmol/L
Fasting blood glucose	Glucose, Fasting Serum	GLUCF	< 40mg/dL	< 40mg/dL	< 2.2mmol/L	> 250mg/dL	> 250mg/dL	≥ 14.0mmol/L
Cholesterol	Cholesterol, Total (TC)	CHOL				> 400mg/dL	> 400mg/dL	> 10.3mmol/L
Triglycerides	Triglycerides, Fasting	TRIGF				> 500mg/dL	> 500mg/dL	> 5.7mmol/L

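### SAP 7.7 and 7.7.2 name different, unreconciled sources for laboratory marked abnormalities, and no visible output screens at the protocol's joint limits for potential DILI

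*SAP*

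**What the plan says.** **Marked abnormalities.** SAP section 4.2 lists the description and incidence of laboratory test marked abnormalities as a secondary safety endpoint. Two sources define the term:

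- SAP section 7.7, in its opening paragraph, takes values that are critically "out of range per the central laboratory manual, will be summarized descriptively". Protocol section 8.4.3 uses the same source.
- SAP section 7.7.2, the laboratory section, begins "Laboratory marked abnormalities as identified using pre-defined criteria" and refers to Appendix 4. That appendix is introduced as "Thresholds for defining markedly abnormal laboratory analyte values (per National Cancer Institute Common Terminology Criteria for Adverse Events", version 4.0.

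SAP section 7.1 sets out the modifications to the protocol's analyses. It clarifies what the description of marked abnormalities means (descriptive statistics) but says nothing about how one is defined.

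**Liver limits.** Appendix 4 flags AST or ALT above 5.0 x ULN and total bilirubin above 3.0 x ULN, each in its own row. Protocol section 6.6 defines potential DILI by three conditions that must all hold:

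- "A serum AT (ALT or AST) elevation" above 3 times ULN;
- total bilirubin above 2 "times ULN, without initial findings suggestive of cholestasis";
- "No other immediately apparent possible causes of AT elevation and hyperbilirubinemia".

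It adds: "All occurrences of potential DILIs, meeting the defined criteria, must be reported as SAEs".

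**The concern.** A single incidence table should rest on one rule. Here a programmer working from SAP section 7.7 would need the laboratory manual's critical limits, while one working from section 7.7.2 would use Appendix 4. If the two sets of limits differ, the same data give two tables and the plan does not say which is the planned one.

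The liver rows raise a second question. Reporting of potential DILI is mandatory but starts with the investigator recognising it. The central chemistry panel (protocol section 5.3.6.1) contains ALT, AST, alkaline phosphatase and total bilirubin, so a check on completeness is possible from data already collected. The Appendix 4 rows are set above the protocol's DILI limits and are never combined, so they do not provide that check.

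**Working it through.** The plan states no figure for this point. The check compares definitions and applies the two liver rules to illustrative values.

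**Step 1: the two definitions side by side.**

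| Place | Source of the cut-off |
|---|---|
| Protocol 8.4.3 | Central laboratory manual, critical range |
| SAP 7.7 | Central laboratory manual, critical range |
| SAP 7.7.2 | Pre-defined criteria in Appendix 4 |
| SAP Appendix 4 | Fixed thresholds attributed to CTCAE version 4.0 |
| SAP 7.1 | No mention of a change of definition |

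The manual's limits are not available, so the cut-offs cannot be compared analyte by analyte. The effect of one reclassified subject in a planned arm of 35 is 1/35 = 2.9 percentage points. This gives the scale only; it does not estimate how many subjects are affected.

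**Step 2: liver rules.** With AT = the ALT or AST value and TB = total bilirubin, both in multiples of ULN:

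- Protocol 6.6, laboratory limits: AT > 3 and TB > 2.
- Appendix 4: a flag if AT > 5; a separate flag if TB > 3.

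| AT / TB | Meets 6.6 limits | AT flag | TB flag |
|---|---|---|---|
| 3.0 / 2.0 | no | no | no |
| 3.5 / 2.2 | yes | no | no |
| 4.9 / 2.9 | yes | no | no |
| 5.0 / 3.0 | yes | no | no |
| 5.1 / 2.5 | yes | yes | no |
| 4.0 / 3.5 | yes | no | yes |
| 6.0 / 4.0 | yes | yes | yes |

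The unflagged region is therefore 3 < AT ≤ 5 together with 2 < TB ≤ 3. Beyond it, at least one analyte is flagged, but the combination is never tested.

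**Step 3: do other visible outputs cover that region?**

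- The value listing in SAP 7.7.2 is limited to subjects with a marked abnormality of the analyte concerned, so subjects in the region are not listed. Where only one analyte is flagged, only that analyte is listed.
- The summaries over time give a maximum for each analyte. They cannot show that two elevations belong to the same subject.
- The AE and SAE tables and listings (SAP 7.7.1.1) show what investigators reported. DILI is not among the events of special interest in SAP 7.7.1.2.

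**Step 4: is Appendix 4 ready to be the only definition?** One row is not. For the urine protein/creatinine ratio, the two conventional limits are 3500 mg/mg and 3.5 g/mg, which are the same quantity (3.5 g = 3500 mg). The SI limit is 395 mg/mmol. With creatinine at 113.12 mg/mmol, 395 / 113.12 = 3.49 mg/mg. The ratio is 3500 / 3.49, or about 1000. A programmer using the conventional column would apply a limit about 1000 times higher than one using the SI column.

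**The case against.** The strongest reply has four parts.

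1. **Section 7.7 is introductory text carried over from the protocol, and 7.7.2 is the operative section.** The SAP's document history shows that the Appendix 4 criteria were added in version 3.0, and a programmer would most naturally follow the specific section. This is probably what was intended, and it makes the repair simple. It does not settle the matter, because no text gives 7.7.2 precedence and section 7.1, the place for declaring such a change, is silent.

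2. **A conflict in the numbers has not been shown.** This stands. A reader might infer that the two definitions are incompatible, but the manual's critical limits could coincide with Appendix 4. The documents support only that two sources are named and not reconciled.

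3. **Appendix 4 was not designed to detect DILI.** This also stands. It sets single-analyte severity limits, whereas potential DILI is an SAE trigger whose last condition needs clinical judgement. DILI is neither a named endpoint nor an event of special interest, and neither document promises a laboratory screen, so its absence contradicts nothing. The point is a gap in cross-checking.

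4. **The visible text may be incomplete.** SAP section 8.7 refers to sponsor safety conventions and a compound-specific supplement that are not provided, and some blocks after section 7.7.3 are redacted. The gap is therefore stated for the visible outputs only.

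**Conclusion.** Both parts hold in limited form. First, SAP 7.7 and 7.7.2 give unreconciled sources for one term, so the incidence of laboratory marked abnormalities is not uniquely defined. The number of subjects affected cannot be estimated; each would move an arm of 35 by 2.9 percentage points. Second, the visible outputs contain no screen at the protocol's joint DILI laboratory limits. A case that the investigator did not report, with ALT or AST above 3 and up to 5 x ULN and bilirubin above 2 and up to 3 x ULN, would not be flagged.

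A reader might go further and infer that the planned outputs cannot show potential DILI at all, or that the trial's data could not confirm complete reporting. The documents do not support either reading. Reported cases appear in the SAE tables and listings, values above 5 x ULN (ALT/AST) or 3 x ULN (bilirubin) are flagged, and the analytes needed for the check are already measured centrally.

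The primary endpoint is unaffected and the study is descriptive. The correction should still be made before database lock, because it concerns a secondary safety endpoint and a mandatory safety report. The conclusion assumes that neither the redacted text nor the sponsor's safety conventions already supply a governing definition or a joint liver listing.

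**What to change.** - Correct the urine protein/creatinine row of Appendix 4 first, so that its conventional and SI limits express the same threshold.
- In SAP 7.7, name Appendix 4 as the single governing definition and delete the laboratory-manual wording. Declare the departure from protocol 8.4.3 in SAP 7.1.
- Add to SAP 7.7.2 a by-arm listing of subjects who meet the protocol 6.6 laboratory limits (ALT or AST > 3 x ULN and total bilirubin > 2 x ULN), showing alkaline phosphatase and sample dates. State a time window within which both elevations must occur. Do not require the same sample, because protocol 6.6 does not.
- Reconcile that listing against SAEs reported as potential DILI before database lock.

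The cost is SAP wording, one listing and one reconciliation check, with no new data. The downside is that the listing identifies candidates only: a few flagged subjects will have another evident cause and need a comment, and elevations between sampled visits remain unseen.

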7.7.1 Adverse Events Analysis

7.7.1.1 All Adverse Events

Adverse Events are recorded by the investigators on the Serious and Non-Serious Adverse Event page(s) of the CRF. All investigators are required to report the nature, the onset and resolution date, intensity, action taken, treatment required for event, and their opinion regarding the relationship between the AE and the study medication.

Summary information (the number and percent of subjects by treatment) will be tabulated for:

- All AEs including clinical and laboratory adverse events.
- Most common AEs (reported in at least 5% of subjects in any treatment group).
- Treatment Related AEs.
- Serious adverse events (SAE).
- SAEs/AEs leading to discontinuation of study therapy.
- Adverse events categorized by severity.
- Serious adverse events and related serious adverse events with death as an outcome following EudraCT.

Summaries will be presented by treatment groups and categorized by System Organ Classes (SOCs) and Preferred Terms (PTs).

Listings for deaths, AEs, SAEs, and AEs/SAEs leading to discontinuation of study therapy will be provided. Detailed conventions for counting events are provided in [Section 8.8](#).

Incidence rates for AEs/SAEs will be provided, where exposure (in days) of a subject is calculated from the randomization to the event date, or the last dose date + 56 whichever is the earlier. The incidence rate = $100 * \text{number of subjects with specified AEs/SAEs} / \text{total exposure in years}$ which is computed as total exposure in days divided by 365.25. For a subject who had multiple occurrences of a specific event, the first occurrence date of the event will be the event date.

7.7.1.2 Events of Special Interest

The following adverse events of special interest, as obtained from the additional CRF pages or appropriate source documentation will be listed or both listed and summarized by treatment group, as specified below:

- Serious Infections (listing and summary).
- PTLD (listing).
- PML (listing).

- Malignancies (other than PTLD) including non-melanoma skin carcinomas (listing).
- TB Infections (serious and non-serious) (listing).
- CNS Infections (serious and non-serious) (listing).
- Viral Infections (serious) (listing and summary).
- Infusion related reactions within 24 hours since belatacept infusion (listing and summary).

The conventions for counting adverse events are provided in [Section 8.8](#). Listings of all adverse events will also be based on all available data up to database lock.

Incidence rates will be calculated for SAEs and AEs of clinical interest for the Month 24 analysis. The numerator is the number of subjects having the first occurrence of the event within the period specified. The denominator is the overall total exposure in years (total exposure days/365.25) within the period specified. However, for these summaries subjects experiencing the event of interest will have their exposure censored at the time of the first occurrence of the event. The resulting incidence rate is multiplied by 100 to express the rate per 100 person-year of exposure. Subjects for whom the time of onset of the first occurrence of the AE of interest is in a given interval will not be included in the exposure and incidence rates in later intervals.

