**Investigational Product(s) Dose and Mode of Administration, Duration of Treatment:**

**Belatacept** will be administered via intravenous (i.v.) infusion according to the following regimen:

Subjects randomized to the belatacept treatment group in the study will receive a belatacept regimen consisting of 10 mg/kg i.v. on Day 1 (started at least 12 but no more than 24 hours after completion of the initial induction dose of Thymoglobulin) and on Week 1 (Day 7), and then at weeks 2, 4, 8 and 12 post-transplant. After 3 months (Week 12), subjects will receive belatacept at the maintenance dose of 5 mg/kg i.v. every 4 weeks until completion of the trial.

**Thymoglobulin** will be administered via i.v. infusion according to the following regimen:

All subjects will receive Thymoglobulin in a dose of up to 1.5 mg/kg i.v. on Day 1 (Day of Transplant) and daily thereafter (or less frequently, as tolerated) to reach a total cumulative dose between 3.0 and 5.5 mg/kg. Premedication with i.v. methylprednisolone is required; as well as acetaminophen and/or antihistamine, per local practice, are recommended to reduce the risk of infusion reactions.

**Everolimus (EVL)** will be administered orally according to the following regimen:

Subjects randomized to receive EVL will receive an initial dose of 3.0 mg/day (1.5 mg bid) starting on Day 3. In subjects who experience delayed graft function (DGF), defined as the requirement for acute dialysis during the first post-transplant week, initiation of EVL may be delayed up to Day 7. In order to guide dose modifications, EVL pre dose trough levels should be obtained from the local laboratory per the protocol required schedule and 4 to 5 days after any change in dose. The dosing will be adjusted to keep pre-dose (C0) levels at 6 to 10 ng/mL for the initial 3 months post transplantation and at 4 to 8 ng/mL after 3 months and for the remainder of the study.

**Tacrolimus (TAC)** will be administered orally according to the following regimen:

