### **4.3 Selection and Timing of Dose for Each Subject**

#### **4.3.1 *Belatacept***

Subjects randomized to a belatacept treatment group in the study will receive a belatacept regimen consisting of 10 mg/kg i.v. for the first 3 months post transplant. (Refer to [Table 5.1-4](#)) After 3 months (week 12), subjects will receive belatacept at the maintenance dose of 5 mg/kg i.v. every 4 weeks until completion of the trial. (Refer to [Table 5.1-5](#)) The entire belatacept infusion should be administered over a period of 30 minutes.

The initial infusion of belatacept should be started at least 12 but no more than 24 hours **after** completion of the initial induction dose of Thymoglobulin. If the Week 1 dose of belatacept will be infused on the same day as a dose of Thymoglobulin, the belatacept infusion must be completed: a) at least 12 hours **prior to** the initiation of the methylprednisolone premedication dose for the Thymoglobulin infusion; or b) at least 12 hours **after** completion of the Thymoglobulin infusion. To facilitate scheduling, infusion windows are permitted for belatacept infusion ([Table 5.3.2-1](#)).

Based upon Pharmacodynamic and Pharmacokinetic modeling of receptor occupancy of CD86, administration of the second belatacept dose at the end of Week 1 (Day 7, +/- 1 day) will ensure that subjects achieve receptor occupancy of > 90% through Week 4 post transplant, just as the Day 5 dose, in the phase 3 studies, was shown to achieve.

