#### **4.3.2 Thymoglobulin**

All subjects will receive Thymoglobulin in a dose of up to 1.5 mg/kg by i.v. infusion on Day 1 (Day of Transplant) and daily thereafter (or less frequently, as tolerated) to reach a total cumulative dose between 3.0 and 5.5 mg/kg. Premedication with i.v. methylprednisolone (as per [Section 4.3.5](#)) is required, as well as acetaminophen and/or antihistamine, per local practice, are recommended to reduce the risk of infusion reactions.

The initial Thymoglobulin infusion (Day1) should be administered over a period of at least 6 hours, to be initiated intraoperatively, after premedication with methylprednisolone and prior to vascular reperfusion of the allograft. Subsequent doses should be administered over a period of at least 4 hours, each to begin after methylprednisolone premedication. For subjects randomized to receive belatacept, please refer to [Section 4.3.1](#) for guidance as to the appropriate sequence and timing in which the Thymoglobulin and belatacept doses are to be infused (when both are given on the same day).

At the discretion of the Investigator, Thymoglobulin doses may be given daily (or less frequently, as tolerated), as long as the total number of days of induction does not exceed 10 days and the cumulative dose does not exceed 5.5 mg/kg.

Prior to administration of each dose, hematology lab values must be reviewed by the Investigator. If the absolute lymphocyte count is < 100/mm^3, Thymoglobulin will not be administered any further. If the platelet count is < 80,000/mm^3, the dose of Thymoglobulin will be decreased by 50%. If the platelet count is < 50,000/mm^3, Thymoglobulin will be withheld until laboratory values return to acceptable levels for Thymoglobulin infusion.

Thymoglobulin should be administered using a 0.22-micron filter through a peripheral or central vein only. Each reconstituted Thymoglobulin vial (25 mg or 5 mg/mL) should be diluted to a recommended volume of 50 mL with NSS or D5W.

For additional information on Thymoglobulin, see the package insert.

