## 6 ADVERSE EVENTS

An *Adverse Event (AE)* is defined as any new untoward medical occurrence or worsening of a preexisting medical condition in a clinical investigation subject administered an investigational (medicinal) product and that does not necessarily have a causal relationship with this treatment. An AE can therefore be any unfavorable and unintended sign (such as an abnormal laboratory finding), symptom, or disease temporally associated with the use of investigational product, whether or not considered related to the investigational product.

The causal relationship to study drug is determined by a physician and should be used to assess all adverse events (AE). The causal relationship can be one of the following:

Related: There is a reasonable causal relationship between study drug administration and the AE.

Not related: There is not a reasonable causal relationship between study drug administration and the AE.

The term "reasonable causal relationship" means there is evidence to suggest a causal relationship.

Adverse events can be spontaneously reported or elicited during open-ended questioning, examination, or evaluation of a subject. (In order to prevent reporting bias, subjects should not be questioned regarding the specific occurrence of one or more AEs.)

Note: Acute rejection will not be reported as an AE or SAE in this study. These events will be collected on separate CRFs.

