APPENDIX 3 LIST OF PERI-INFUSIONAL EVENTS

List of peri-infusional events (infusion related reactions) is obtained from the preferred terms that correspond to the BMS predefined list of MedDRA preferred terms (Infusion -related reactions-EU- SMQ_CODE BMS03061). The peri-infusional events are those occurring within 24 hours of Belatacept administration. The latest MedDRA Version of the list of events at the time of the database lock will be used.

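### The peri-infusional event count has no visible rule for a Thymoglobulin infusion in the same 24-hour window, which under daily induction with three or more doses always occurs at the first belatacept infusion

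*SAP*

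**What the plan says.** SAP 7.7.1.2 (Events of Special Interest) lists and summarises "Infusion related reactions within 24 hours since belatacept infusion (listing and summary". SAP Appendix 3 takes the terms from a sponsor "predefined list of MedDRA preferred terms" and adds the timing condition: "The peri-infusional events are those occurring within 24 hours of Belatacept administration". Neither place excludes, flags or separately counts events that also follow a Thymoglobulin infusion.

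The protocol synopsis and section 4.3.1 require the first belatacept infusion to be "started at least 12 but no more than 24 hours after completion of the initial induction dose of Thymoglobulin". On Thymoglobulin, Protocol 4.3.2 says "The initial Thymoglobulin infusion (Day1) should be administered over a period of at least 6 hours", and that "Thymoglobulin doses may be given daily (or less frequently, as tolerated"), within a 10-day limit. All subjects in both arms receive it. Methylprednisolone premedication is required to lower the risk of infusion reactions (Protocol 4.3.2 and 4.3.6), so the protocol expects them.

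On causality, Protocol section 6 says "The causal relationship to study drug is determined by a physician". Protocol 4.1.1 names Thymoglobulin, as well as belatacept, as an investigational product. Protocol 6.7.1 lists infusion reactions as an event of special interest without tying them to belatacept.

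**The concern.** The definition rests on a term list and a clock that starts with belatacept. If another drug known to cause infusion reactions is running in the same 24 hours, the count cannot tell the two apart. A causality entry of related to study drug does not settle it, because both products are study drugs.

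The window at issue is the first belatacept infusion, which almost every subject in that arm passes through. The incidence rate in SAP 7.7.1.2 takes each subject's first occurrence and censors exposure there. One Thymoglobulin reaction at that point makes the subject an event, however uneventful the later infusions are. TAC-arm subjects receive the same induction, but their infusion reactions can appear only in the general adverse event tables. A reader of the clinical study report could take the belatacept figure as a property of belatacept when part of it may reflect induction.

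**Working it through.** The plan states no figure to reproduce, so the check is an overlap calculation from the protocol's own timings.

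**Inputs**
- First Thymoglobulin infusion: length L1, at least 6 h (Protocol 4.3.2).
- Later Thymoglobulin infusions: at least 4 h (Protocol 4.3.2).
- First belatacept infusion: starts 12 to 24 h after the first Thymoglobulin infusion ends, and runs 30 min (Protocol 4.3.1).
- Counting window: 24 h (SAP 7.7.1.2 and Appendix 3).
- Thymoglobulin: up to 1.5 mg/kg per dose, 3.0 to 5.5 mg/kg in total (Protocol 4.3.2).
- Assumptions: daily means exactly 24 h between starts; belatacept start times are spread evenly over the permitted range; the window runs from the start of belatacept to 24 h after the end of its infusion.

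**Formula.** Take hour 0 as the start of Thymoglobulin dose 1. Belatacept starts at b, between L1 + 12 and L1 + 24. The window is from b to b + 0.5 + 24. With L1 = 6, b lies between 18 and 30. A Thymoglobulin dose starting at hour t is in the window if b ≤ t ≤ b + 24.5.

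**Three or more daily doses (t = 24, 48, ...).** Dose 2 is in the window for b ≤ 24. Dose 3 is in the window for b ≥ 48 − 24.5 = 23.5. Together they cover every b from 18 to 30, so the share is 100%. It is also 100% for L1 = 8, 10 and 12 h.

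**Two daily doses (t = 24 only).**
- L1 = 6 h: a start in the window needs b ≤ 24, so (24 − 18)/12 = 50%. Any overlap needs b ≤ 24 + 4 = 28, so (28 − 18)/12 = 83%.
- L1 = 8 h (b from 20 to 32): (24 − 20)/12 = 33% and (28 − 20)/12 = 67%.

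**Every 48 h (t = 48), L1 = 6 h.** This needs b ≥ 23.5, so (30 − 23.5)/12 = 54%. If the window is counted from the start of belatacept instead of the end, it is (30 − 24)/12 = 50%, and the three-dose result stays at 100%.

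**How many doses are needed.** 3.0/1.5 = 2, so a two-dose course is possible only at exactly 3.0 mg/kg. Any larger total needs at least 3 doses, and 5.5/1.5 = 3.67 means at least 4.

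**Which belatacept infusions are touched.** The schedule has 6 infusions through Week 12 (Day 1 and Weeks 1, 2, 4, 8, 12) and (104 − 16)/4 + 1 = 23 from Week 16 to Week 104, so 29 in all. At 1.5 mg/kg daily, induction ends by Day 2 to 4 and only the first of the 29 is affected. The Week 1 infusion (Day 7 ± 1) is affected only if induction continues to about that day. Protocol 4.3.1 allows both drugs on the same day then, with a 12 h gap, which is shorter than the 24 h window.

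**What cannot be caught.** Reactions during Thymoglobulin dose 1 precede belatacept by at least 12 h, so they fall outside a window counted since belatacept. The exposure is to reactions to dose 2 or 3.

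**The case against.** The strongest reply is that the SAP label is temporal. It counts events after belatacept and does not call them caused by belatacept. The overlap mainly concerns one infusion of 29, and any bias runs against the experimental drug. All adverse events are also tabulated by preferred term in both arms and listed (SAP 7.7.1.1), so with about 35 subjects per arm the early events can be read case by case. Supplementary forms or source documents for events of special interest (Protocol 6.7.1) and the sponsor's safety conventions (SAP 8.7) might separate the two drugs; neither can be seen. The term list is not shown either, so it is an assumption that Thymoglobulin reactions map to it.

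Most of this stands as a limit on size and certainty. It does not remove the gap: the summary as specified has no proximity rule, and its first-occurrence rate gives the first infusion more weight than one in 29 suggests.

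A reader might also infer that the plan builds in a one-sided comparison between arms, since the SAP's general endpoint section says the groups are compared on all secondary endpoints. The documents do not support that. SAP 7.1 restricts treatment differences to the endpoints specified for them, SAP 7.7.1.2 specifies none for this event, and SAP 7.7 rules out testing of adverse event frequencies.

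**Conclusion.** The point holds as a gap in a secondary safety summary that should be closed. With three or more daily Thymoglobulin doses, one starts in the 24 hours after the first belatacept infusion at every permitted start time. For two daily doses with a 6 h first infusion the share is about 50% by start and 83% by overlap, and for 48-hourly dosing about 54%. These shares assume regular spacing and evenly spread start times.

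Three stronger readings should be avoided:
- That most two-dose subjects have a new Thymoglobulin infusion start in the window. By that test it is half at best; a majority appears only when an infusion already under way is counted.
- That a number of falsely counted subjects can be stated. That needs a Thymoglobulin reaction rate, which the documents do not give, and the actual dosing pattern of each subject.
- That the TAC arm's reactions go unreported. They remain in the general adverse event tables; what is absent from the visible plan is an infusion-reaction count.

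**What to change.** In SAP 7.7.1.2 and Appendix 3:

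1. Use recorded dosing dates (Protocol 4.5 requires them on the eCRF) to flag each event where Thymoglobulin was given on the same, previous or next calendar day as belatacept.
2. Summarise separately (a) belatacept infusions with such proximity and (b) those without. Apply the date rule itself and not a visit cut-off such as Week 2 onward: a Week 1 infusion after a short induction belongs in (b), and Thymoglobulin may be given again for rejection (Protocol 5.3.10).
3. Report both. Describe (b) as free of Thymoglobulin overlap, not as the full belatacept-attributable rate, because reactions at first exposure may be genuine belatacept reactions.
4. Add a descriptive count of the same terms within 24 h (or on the same or next calendar day) of Thymoglobulin infusions in both arms. Note that post-infusion adverse event contact is scheduled for belatacept subjects only (Protocol Tables 5.1-2 and 5.1-3), so ascertainment is unequal and the two figures are not strictly comparable.

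The cost is SAP wording and one or two extra tables, with no new data. The downside is that (b) omits most first-exposure infusions: any that starts within the permitted 24 h of the end of Thymoglobulin dose 1 meets the same-or-previous-day condition. Those infusions are shown in (a).
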